## 7.6.2 LABORATORY TESTS

Laboratory test results will be summarized with descriptive statistics for each treatment group at Screening and Final Evaluation Visit. Change from Screening to Final Evaluation Visit also will be summarized for continuous test results.

Shift tables will be presented to summarize laboratory test results at Screening and Final Evaluation Visit. Normal ranges established by the central laboratory will be used to

determine shifts. A listing of all out-of-range laboratory test results at any evaluation will also be provided. Determination of clinical significance for all out-of-range laboratory values will be made by each investigator and included in the listing. In addition, a listing of all clinically significant laboratory test results will be provided.

[figure not shown]
UPTs will be summarized for all treated subjects in the category of WOCBP by treatment group and presented in the data listings.

#### 7.6.3 VITAL SIGNS AND PHYSICAL EXAMINATION

Vital signs and abnormal findings from the physical examination will be summarized with descriptive statistics for each treatment group by visit.

#### 7.6.4 INJECTION SITE EVALUATION

Outcomes of the injection site evaluations will be tabulated by visit.

#### 7.6.8 CONCOMITANT THERAPIES/MEDICATIONS

[figure not shown]
Concomitant therapies/medications used at Screening and at each trial visit will be coded using the World Health Organization (WHO) drug dictionary and summarized by treatment group, Anatomical Therapeutic Chemical (ATC) second level term, and preferred name for the Safety population.

[figure not shown]
#### 7.6.9 ECG

The results of the ECG data will be tabulated by visit.

## 7.7 SAMPLE SIZE AND POWER CONSIDERATIONS

Estimates of treatment efficacy taken from trial RT002-CL002 show that a sample size of
200 and 100 for DaxibotulinumtoxinA 40 U for injection and placebo, respectively,

#### 9 RECORDS MANAGEMENT

#### 9.1 DATA COLLECTION

For this trial, all protocol-specified data will be recorded in the source documents, and data will be entered on the CRFs from the source documents. In addition to signature confirmation that a subject meets the study eligibility criteria, upon each subject's completion of the trial, the Investigator will sign a statement indicating that all pages of the subject's case report have been reviewed. Signature stamps and "per signatures" are not acceptable.

It is Revance's policy that the trial data be verifiable with the source data that necessitates access to all original recordings, laboratory reports, and other records for each subject. The Investigator must therefore agree to allow access to subjects' records, and source data must be made available for all trial data. Subjects (or their legal representatives) must also allow access to their medical records. Subjects will be informed of the importance of increased record access and permission granted by signature on the informed consent document prior to Screening.

Checks will be performed to ensure the quality, consistency, and completeness of the data. Instances of missing or un-interpretable data will be resolved with the Investigator or Study Coordinator. Data queries will be sent to the trial center. Site personnel will be responsible for providing resolutions to the data queries and for correcting the CRFs, as appropriate. All unused Revance source documents and binders must be returned to Revance upon completion of the trial.

The Investigator must keep written or electronic source documents for every subject participating in the clinical trial. The subject file that identifies the study in which the subject is participating must include the subject's available demographic and medical information including:

- Name
- Contact information
- Date of birth
- Sex
- Medical history
- Concomitant diseases
- Concomitant therapies/medication
- Study visit dates
- Performed examinations, evaluations, and clinical findings

- Investigational product administration
- AEs, SAEs, or pregnancy (as applicable)

Additionally, any other documents with source data, especially original printouts of data that were generated by technical equipment must be included in the subject's source document (e.g., laboratory value listings). All these documents must have at least the subject's initials, trial number, and the date of the evaluation.

The data recorded during the course of the trial will be documented in the CRF and/or the trial-specific forms. Before or at study termination, all data must be forwarded to Revance. The data will then be recorded, evaluated, and stored in anonymous form in accordance with data-protection regulations.

Subjects will authorize the use of their protected health information during the informed consent process in accordance with the applicable privacy requirements. Subjects who deny permission to use and disclose protected health information will not be eligible to participate in the trial. The Investigator will ensure that the trial documents forwarded to Revance, and any other documents, contain no mention of subject names.

Any amendments and corrections necessary will be undertaken in both the source documents and CRFs (as appropriate) and countersigned by the Investigator, or documented designee, stating the date of the amendment/correction. Errors must remain legible and may not be deleted with correction aids. The Investigator must state his/her reason for the correction of any data. In the case of missing data/remarks, the entry spaces provided in the CRF should be cancelled out so as to avoid unnecessary follow-up inquiries.

Regulatory authorities, the IRB/IEC and/or the Revance's Quality Assurance group (or designee) may request access to all source documents, CRFs, and other trial documentation for on-site audit or inspection. The Investigator must guarantee direct access to these documents. CRFs will be kept by Revance or an authorized designee in a secured area. Clinical data will be recorded in a computer format for subsequent statistical analyses. Data files will be stored on electronic media with a final master data file kept by Revance after descriptive and statistical analyses and reports have been generated and are complete.

#### 9.2 FILE MANAGEMENT AT THE TRIAL CENTER

It is the responsibility of the Investigator to ensure that the trial center file is maintained in accordance with ICH Guidance for Industry E6 Good Clinical Practice: Consolidated Guidance, Section 8 – Essential Documents for the Conduct of a Clinical Trial.

[figure not shown]
#### 9.3 RECORDS RETENTION AT THE TRIAL CENTER

It is a Revance requirement that all Investigators participating in clinical studies maintain detailed clinical data for one of the following periods:

- Country-specific requirements, or
- A period of at least 2 years following the last approval of a marketing application approved by a Regulatory Authority in an ICH region or until there are no pending or contemplated marketing applications in an ICH region, or,
- A period of two years after Revance notifies the Investigator that the data will not be submitted for review by any Regulatory Authority

[figure not shown]
The Investigator must not dispose of any records or essential documents relevant to this trial without either (1) written permission from Revance, or (2) providing an opportunity for Revance to collect such records. The Investigator shall take responsibility for maintaining adequate and accurate electronic or hard copy source documents of all observations and data generated during this trial. Such documentation is subject to inspection by Revance and relevant regulatory agencies. If the Investigator withdraws from the trial (e.g., relocation, retirement) all trial-related records should be transferred to a mutually agreed upon designee. Notice of such transfer will be provided to Revance in writing.

[figure not shown]
All aspects of the trial will be monitored by Revance or authorized representatives of Revance according to Good Clinical Practices (GCP) and Standard Operating Procedures
(SOPs) for compliance with applicable government regulations, (i.e., Informed Consent
Regulations and Institutional Review Board regulations).

[figure not shown]

[figure not shown]
## 11 ETHICS AND RESPONSIBILITY

[figure not shown]
This trial must be conducted in compliance with the protocol, the ICH Guidance for Industry E6 Good Clinical Practice: Consolidated Guidance and the applicable regulatory requirements. Investigators must submit all essential regulatory documentation, as required by local and national regulations (including IRB/IEC approval of the protocol and informed consent form) to Revance before investigational product will be shipped to the trial center.

[figure not shown]

[figure not shown]

[figure not shown]

[figure not shown]

[figure not shown]

[figure not shown]

[figure not shown]

[figure not shown]

Revance Therapeutics CONFIDENTIAL Page 91 of 94

Revance Therapeutics CONFIDENTIAL Page 92 of 94

Revance Therapeutics CONFIDENTIAL Page 93 of 94

Version: Amendment 1, 07 November 2016

Revance Therapeutics CONFIDENTIAL Page 94 of 94

1. INTRODUCTION

This statistical analysis plan (SAP) describes the objectives of the study and the efficacy and safety assessments that are collected. The primary, secondary, and exploratory efficacy endpoints and the safety endpoints are defined, and the statistical methods used to analyze them are presented. Table shells for the planned end-of-text tables, figures, and listings are included following the text of the SAP.

2. STUDY OBJECTIVES

The study objective is to evaluate the efficacy and safety of a single treatment of DaxibotulinumtoxinA for Injection for the treatment of moderate to severe glabellar lines compared to placebo.

2.1. Overall Study Design and Plan

[figure not shown]
This is a phase 3, double blind, placebo-controlled, multi-center trial to evaluate the efficacy and safety of a single intramuscular (IM) treatment of DaxibotulinumtoxinA for Injection for the temporary improvement in the appearance of glabellar lines in adults compared to a placebo.

The duration is up to 38 weeks on trial, including a screening period of up to two weeks followed by a single treatment and a follow-up period of up to 36 weeks post-treatment. All patients will be followed for at least 24 weeks post-treatment. Starting at Week 24 post-treatment, patients will be followed until their wrinkle severity in the glabellar lines at maximum frown returns to baseline in both the Investigator Global Assessment-Facial Wrinkle Severity (IGA-FWS) and Patient Facial Wrinkle Severity (PFWS) assessments.

2.3. Determination of Sample Size

2.4. Treatments Administered

Approximately 300 adult patients with moderate to severe glabellar lines will be enrolled.

3. Efficacy and Safety Assessments

The primary efficacy assessments will include investigator assessment of glabellar line severity and glabellar line improvement, and patient assessment of glabellar line severity and improvement.

3.1. Frown Wrinkle Severity – Patient and Investigator Global Assessment

Frown wrinkle severity is assessed by both the patient (Patient Frown Wrinkle Severity [PFWS]) and the investigator (Investigator Global Assessment Frown Wrinkle Severity [IGA-FWS]) using the same 4-point rating scale, as shown in Table 3.1.1-1.

[figure not shown]
The severity is assessed at maximum frown and at rest after maximum frown by both the patient and the investigator. The scores range from 0 = none to 3 = severe.

[figure not shown]
Table 3.1.1-1 Frown Wrinkle Severity

Rating Score	Frown Wrinkle Severity	Description
0	None	No wrinkles
1	Mild	Very shallow wrinkles
2	Moderate	Moderate wrinkles
3	Severe	Deep wrinkles

3.1.1. Primary Efficacy Endpoint

The **primary efficacy endpoint** is derived from the maximum frown scores obtained at Week 4, and is defined as achieving a score of 0 or 1 (none or mild) and an improvement of at least two points from baseline on both the IGA-FWS and PFWS scales concurrently. The response will be abbreviated as "2-point composite response" henceforth.

3.2. Additional Assessments

3.2.1. Patient Diary

Patients will capture their assessment of the appearance of the lines at maximum frown, in a diary for the initial 2-week post treatment period, using the 4 point severity scale given in Table 3.1.1-1.

3.2.2. Patient Global Satisfaction with Treatment Questionnaire

Patients will be asked how satisfied or dissatisfied they are with the treatment results using a 7 point scale at Week 4. This treatment questionnaire will be based on how the treated area of the face looks (see Table 3.2.2-2).

 Table 3.2.2-2
 Global Satisfaction with Treatment Questionnaire Scale

[figure not shown]
Rating Score	Wrinkle Improvement
0	Very Dissatisfied
1	Dissatisfied
2	Somewhat Dissatisfied
3	Neither Satisfied Nor Dissatisfied
4	Somewhat Satisfied
5	Satisfied
6	Very Satisfied

3.2.3. Global Aesthetic Improvement Scale

The Investigator and patient will assess the visual appearance (at maximum frown and at rest after maximum frown) of the glabellar line improvement from the baseline condition using the following 7 point severity Global Aesthetic Improvement Scale (GAIS, Table 3.2.3-3).

[figure not shown]
 Table 3.2.3-3
 Global Aesthetic Improvement Scale

Rating Score	Wrinkle Improvement
-3	Very Much Worse
-2	Much Worse
-1	Worse
0	No Change
1	Improved
2	Much Improved
3	Very Much Improved

3.2.5. Facial Age Self Evaluation

Patients will rate their perceived age on a Facial Age Self Evaluation (FASE) questionnaire and rate their perception of how old they think they look following the treatment (older than actual age, younger than actual age, actual age). These responses will be used as exploratory endpoints.

3.3. Safety Assessments

3.3.1. Adverse Events

All adverse events (AEs) will be recorded and classified on the basis of MedDRA terminology. AE severity will be graded as mild, moderate, or severe as defined in Section 6.1.2 of the protocol. AEs with an onset on or after the date and time of study treatment will be Treatment-emergent.

The safety endpoints derived from the AEs are:

- Frequency, severity and relationship to study drug of treatment-emergent adverse events during the first four weeks post treatment and the overall study duration
- Frequency, severity and relationship to study drug of treatment-emergent serious adverse events during the first four weeks post treatment and the overall study duration

	İ			

3.3.3. Clinical Laboratory Data

[figure not shown]
As outlined in Table 3.3.3-4, non-fasting samples for hematology, chemistry, coagulation (prothrombin time) and urinalysis will be collected at Screening, Week 4, and at the Final

Evaluation Visit.

Table 3.3.3-4 Clinical Laboratory Tests

Serum Chemistry	Hematology	Urinalysis	Additional Tests
Glucose	Hemoglobin	Overall Assessment	Prothrombin time (PT)
Total bilirubin	Hematocrit	and Clinical	Urine Pregnancy (WOCBP only)
Alkaline	Red Blood Cell	Significance	
phosphatase	Count	S	
Blood urea nitrogen	Platelet Count		
Alanine	Leukocyte Count		
aminotransferase	(total)		
Aspartate	Leukocyte Count		
aminotransferase	(differential)		

WOCBP = Women of child-bearing potential

3.3.5. Vital Signs

Vital signs (i.e., body temperature, respiration rate, sitting radial pulse rate, and sitting systolic and diastolic blood pressures) will be obtained at the Screening and Treatment Visit (pre- and post-treatment), Week 2, Final Evaluation or Early Discontinuation Visits and at any visit where signs or symptoms of botulinum toxicity are reported.

3.3.6. Physical Examination

A physical examination, in addition to vital signs,

, general appearance, skin, neck (including thyroid), eyes, ears, nose, throat, heart, lungs,

abdomen, lymph nodes, and extremities will be conducted at Screening, Week 2 and Final Evaluation or Early Discontinuation Visits. Significant physical examination findings that are present prior to investigational product administration are to be included on the Medical History page.

Significant physical examination findings which meet the definition of an adverse event will be recorded on the adverse event page post-treatment.

3.3.7. 12-Lead ECG

[figure not shown]
At Screening and Week 4, a single standard supine 12-Lead ECG will be obtained.

3.3.8. Injection Site Evaluation

Injection sites will be evaluated at the Screening Visit, Treatment Visit pre- and post-treatment, Follow-up Visits, and Final Evaluation Visit or Early Discontinuation Visit, if applicable. The assessment will be done as a global evaluation of the 5 injection sites (Table 3.3.8-5).

Table 3.3.8-5 Injection Site Evaluation

[figure not shown]
	Present?	
Assessment Descriptor	Yes	No
Erythema		
Edema		
Burning or Stinging (sensation as described by patient)		
Itching (sensation as described by patient)		
Bruising		

4. Statistical Methods

All statistical programming will be performed using statistical analysis system (SAS) version 9.3 or higher.

[figure not shown]
4.1. Analysis Populations

4.1.1. Intent-to-Treat Population

All patients who are randomized and receive treatment will be included in the Intent-to-Treat (ITT) population. The summaries will be by treatment as randomized.

4.1.2. Per Protocol Population

The Per-Protocol (PP) population will include patients from the ITT population who complete the first 4-weeks of the study without a major protocol violation.

4.1.3. Safety Population

All patients who are randomized, receive treatment, and have provided at least one post-treatment safety assessment will be included in the Safety population. The summaries will be by treatment actually received.

4.2. Patient Disposition

The number and percentage of patients who have signed informed consent, been randomized, received treatment, and completed key visits will be tabulated by treatment group overall and by trial center (or pooled center, as appropriate) and included in a listing. Reasons for not completing the study will also be tabulated by treatment group and overall and by trial center using numbers and percentages; this data will also be included in a listing. For those patients who are considered to have failed screening, the reason(s) for failure will be provided in a listing.

The number and percentage of patients included and excluded from the analysis populations (ITT, PP and safety) will be tabulated overall and for each treatment group. Reason(s) for exclusion from each population will be summarized and listed.

Major protocol deviations will be listed and summarized by treatment group.

4.3. Demographic and Baseline Characteristics

Descriptive statistics will be used to summarize demographic and baseline characteristics by treatment group and overall. Continuous variables will be summarized using the number of non-missing observations, mean, standard deviation, median, minimum and maximum. Categorical data will be summarized using the number and percentage of patients in each category. Demographic data include age, sex, race and ethnicity. Age in years will categorized as 18 to 45, >45 to 55, and >55 to 75 for summarizing by treatment group and overall. Baseline characteristics include Prior Botulinum Toxin Type A, Time Since Last Prior Botulinum Toxin Type A Injection, and Fitzpatrick Skin Type, as well as the baseline assessment of the efficacy questionnaires, PFWS, IGA-FWS, FLIS.

and PP populations by randomized treatment; and, for the Safety population by actual treatment received.

4.4. Medical History

Medical history will be classified on the basis of MedDRA terminology, using the latest terminology at the time of database finalization. Medical history will be summarized by treatment group, system organ class, and preferred term, and will be listed.

[figure not shown]
4.5. Prior and Concomitant Medications

[figure not shown]
Prior therapies/medications recorded at Screening but no longer being taken, and concomitant therapies/medications recorded at Screening and still being taken or being taken at each trial visit, will be coded using the World Health Organization (WHO) drug dictionary and summarized by treatment group and overall, Anatomical Therapeutic Chemical (ATC) second level term, and preferred name for the Safety population. Prior and concomitant medications will be summarized separately.

[figure not shown]
4.6. Efficacy Analyses

[figure not shown]
Descriptive statist	cics will be provide	led for all efficac	y variables at all	timepoints by	y treatment
group.					

[figure not shown]
4.6.1. Primary Efficacy Analysis
The proportion of patients who have a 2-point composite response at Week 4 will be compared
between daxibotulinumtoxinA and placebo
. As a sensitivity analysis, the primary analysis
will be repeated
P-values will be provided. The point estimates for the difference
will be calculated
The 2-sided, 95% CIs will be calculated

4.8. Safety Analyses

Safety summaries and analyses will be performed on the safety population. Descriptive statistics will be presented to summarize the safety data.

4.8.1. Extent of Exposure

All patients receive one administration of investigational product. The sum of volume of investigational product injected and the volume of investigational product injected at each of the five injection sites will be summarized by treatment group using descriptive statistics (number of non-missing observations, mean, median, minimum, maximum, and standard deviation).

4.8.2. Injection Site Evaluations

The injection site evaluations will be summarized using number and percentage of patients reporting the presence of each item (Erythema, Edema, Burning or Stinging, Itching and Bruising) by treatment group and visit, as well as the number and percentage of patients with a reaction at any post-treatment visit. In addition, the number and percentage of patients reporting any injection site item will be summarized by treatment group, and by visit as well as at any post-treatment visit. Additionally, the number and percentages of patients with the specified item will be summarized according to the first visit at which the reaction was present.

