# 4.2.5 FINAL EVALUATION VISIT OR EARLY DISCONTINUATION

The following procedures must be performed and recorded at the Final Evaluation Visit for each subject. Following treatment, subjects will be followed for safety until at least Week 24 and up to Week 36 with monthly visits until both IGA-FWS and PFWS scores have returned to baseline. The subject will then have a Final Evaluation Visit.

- 1. Conduct patient education: Discuss the potential effect of DaxibotulinumtoxinA for Injection treatment, explain the PFWS measurement and the categories of the severity assessment scales, and instruct the subjects to consider depth of lines for severity of their glabellar lines. Use the provided Patient Education Brochure
- 2. Measure and record vital signs (body temperature, respiratory rate, sitting radial pulse, and sitting systolic and diastolic blood pressure)

If there are no safety concerns, the subject's participation in the trial is complete at this visit.

After the Final Evaluation Visit, all qualified subjects will have the option to enroll into an open-label, trial to evaluate the long-term safety of repeat use of DaxibotulinumtoxinA for Injection for the treatment of moderate to severe glabellar lines.

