## 4.5.6 INJECTION SITE EVALUATION

Injection sites will be evaluated at the Screening Visit, Treatment Visit pre- and post-treatment (to determine if there is an immediate reaction to the investigational product), Follow-up Visits, and Final Evaluation Visit or Early Discontinuation Visit, if applicable. The assessment will be done as a global evaluation of the 5 injection sites (Table 4).

[figure not shown]

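### The cumulative injection-site reaction count has no visible new-onset rule and no common follow-up window, so it can be modestly distorted

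*SAP*

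**What the plan says.** Five items (erythema, edema, burning or stinging, itching, bruising) are recorded as present or absent. Under SAP 3.3.8, "Injection sites will be evaluated at the Screening Visit, Treatment Visit pre- and post-treatment, Follow-up Visits" and the final or early discontinuation visit. Protocol 4.5.6 gives a purpose for the Day 0 evaluations: "Treatment Visit pre- and post-treatment (to determine if there is an immediate reaction to the investigational product").

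SAP 4.8.2 then plans four kinds of summary:
- the presence of each item "by treatment group and visit";
- for each item, a cumulative count: "as well as the number and percentage of patients with a reaction at any post-treatment visit";
- the same two summaries for any item at all;
- a first-occurrence table, in which "the number and percentages of patients with the specified item will be summarized according to the first visit at which the reaction was present".

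On follow-up, SAP 2.1 states: "All patients will be followed for at least 24 weeks post-treatment". Protocol 4.2.5 has subjects followed "until at least Week 24 and up to Week 36 with monthly visits until both IGA-FWS and PFWS scores have returned to baseline". The synopsis schedules visits at Weeks 1, 2, 4, 8, 12, 16, 20 and 24, then 28, 32 and 36.

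**The concern.** The cumulative table treats presence after injection as a reaction. An erythema or bruise recorded just before the injection, and still there just after it, would count. The data needed to separate the two cases are collected, but the visible text does not use them to define a reaction. The first-occurrence table is looser still: it omits the restriction to post-treatment visits, so a finding at Screening could be tabulated as a first reaction.

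The window is also open-ended. Everyone is scheduled for the same evaluations through Week 24. Beyond that, whether a subject has zero, one, two or three more depends on how long the effect lasts. Randomisation balances what subjects bring to Day 0. It does not balance a number of evaluations that response to treatment determines.

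Other safety data in the SAP are handled differently. Adverse events count as treatment-emergent only with onset at or after treatment, and are reported for the first four weeks and overall (3.3.1). Laboratory results have changes from Screening and shift tables (4.8.4.1). Vital signs and ECG have changes from screening (4.8.6). At stake is whether the cumulative percentage can be read as the rate of reactions to the injection.

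**Working it through.** The documents give no expected rate for these items, so there is no figure to reproduce. All rates below are assumptions, shown as ranges. The inputs from the documents are the visit schedule, the arm sizes (200 and 100) and the follow-up rule.

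**A. Items present before injection.** Let b be the proportion in each arm, equal in expectation under randomisation, with an item present before injection that persists to a later evaluation. Let p1 and p0 be the true new-onset risks on active and placebo.

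Observed risk = b + (1 − b)p, so observed difference = (1 − b)(p1 − p0).

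- No drug effect, p1 = p0 = 10%, b = 5%: 14.5% in both arms, difference 0.
- p1 = 10%, p0 = 6%, b = 1%: 10.9% versus 6.94%. The difference falls from 4.0 to 3.96 points and the ratio from 1.67 to 1.57.
- Same risks, b = 5%: 14.5% versus 10.7%. The difference is 3.8 points and the ratio 1.36.

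Pre-existing items raise both percentages and shrink a true difference. In expectation they do not create one. Chance imbalance remains: at b = 5% the standard error of the arm difference in b is √(0.05 × 0.95 × (1/200 + 1/100)) = 2.7 points.

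**B. Extra late evaluations.** Count the Day 0 post-injection evaluation plus eight follow-up visits, giving 9 through Week 24 and 12 through Week 36. Assume no drug effect on these items and an independent background probability q of any item at each visit. Then:

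Cumulative risk = 1 − (1 − q)^9 through Week 24, and 1 − (1 − q)^12 through Week 36.

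If a share f of active subjects stays for all three extra visits and no placebo subject does, the spurious excess on active is f × [(1 − q)^9 − (1 − q)^12]. In percentage points:

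| q per visit | f = 20% | f = 50% | f = 100% |
|---|---|---|---|
| 0.1% | 0.06 | 0.15 | 0.30 |
| 0.5% | 0.29 | 0.71 | 1.43 |
| 1% | 0.54 | 1.36 | 2.71 |
| 2% | 0.98 | 2.45 | 4.90 |

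For example, at q = 1%: 1 − 0.99^9 = 8.65%, 1 − 0.99^12 = 11.36%, gap 2.71, and half of that is 1.36. If 5% of placebo subjects also stay, 1.36 becomes 1.22. Counting 8 and 11 evaluations instead of 9 and 12 changes 2.71 only to 2.74.

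**C. Scale.** The standard error of an arm difference at 200 and 100 is √(0.10 × 0.90 × 0.015) = 3.7 points at a 10% rate and √(0.20 × 0.80 × 0.015) = 4.9 points at 20%.

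**D. After the change.** Counting only new-onset items restores the difference in A to p1 − p0. Restricting the count to Week 24 or earlier makes the scheduled evaluations equal and takes the excess in B to 0. The flag does not cure B and the window does not cure A, so both are needed.

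**The case against.** A reader might infer that the SAP ignores the pre-injection evaluation altogether. The documents do not support that. Screening and Day 0 pre-treatment are scheduled evaluations, so on a plain reading their findings appear in the by-visit table. What is missing is their use in defining a reaction. SAP sections 4.9.2 to 4.9.4 are not in the public text, so a convention there cannot be ruled out.

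Several mitigating arguments stand:
- SAP 4.8 makes the safety summaries descriptive. No test and no efficacy conclusion rests on this table. The plan is for counts and percentages, so the fall in the ratio in part A concerns a measure that is not planned.
- Protocol 3.4.3 excludes active skin disease, infection or inflammation at the injection sites, which limits b.
- By-visit counts through Week 24 rest on equal scheduled follow-up, and the table "summarized according to the first visit at which the reaction was present" would show first occurrences at Weeks 28 to 36.
- Protocol 6.1 requires a clinically significant post-treatment change in the injection-site evaluation to be reported as an adverse event. That route has an onset rule and a four-week window.
- Part B assumes independence between visits. Findings that recur in the same person would make the excess smaller. The excess counts against the drug, so it does not hide harm.

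These points limit the size of the problem but do not remove it. Per-subject cumulative incidence cannot be recovered from by-visit counts, and findings judged not clinically significant fall outside the adverse event route.

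**Conclusion.** The point holds, and it is minor. On the visible text, the cumulative count includes items that predate the injection and runs over a period that can be longer on active. The first mechanism dilutes a true difference (4.0 to 3.8 points at an assumed 5% prevalence). The second can add an excess on active of about 0.15 to 1.4 points, if background is 0.1% to 1% per visit, half of active subjects stay to Week 36 and no placebo subject does. Larger figures, up to 4.9 points, need 2% background at every visit and every active subject staying. The range of 0.15 to 1.4 points lies below the sampling error of 3.7 points at a 10% rate.

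A reader might go further and conclude that the arm comparison is biased. The documents do not support that statement. The two mechanisms push in opposite directions when the drug has a true excess, neither can be sized from the documents, and the net effect is unknown. The supportable statement is that the cumulative figure can be distorted and is hard to read as a rate of reactions to the injection.

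**What to change.** In SAP 4.8.2:
1. Derive a new-onset flag for each item: absent at the Day 0 pre-injection evaluation and present at a later one. Use it for the cumulative and first-visit tables, and limit the first-visit table to post-treatment evaluations.
2. List separately the subjects whose item was already present before injection. Yes/no recording cannot show worsening, and the flag alone would drop these subjects from view.
3. Report the cumulative count through Week 4, matching the adverse event window, and through Week 24, which every subject is scheduled to reach.
4. Keep the overall-duration count beside these, as the adverse event endpoints do, with a note that follow-up after Week 24 depends on response.

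The cost is SAP wording, one programming flag, a listing and extra table columns, all from data already collected. Reported cumulative percentages will be slightly lower. No trial procedure changes.
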